### **7.5.1.2 Sensitivity Analyses of ORR**

The following sensitivity analyses will be conducted using the primary definition of ORR in the randomized subjects:

- If one stratification variable at IVRS and at baseline (CRF and clinical database) disagrees for at least 10% of the randomized subjects, similar analysis of ORR as primary analysis will be performed using the strata as determined at baseline.
- ORR per BICR for subjects with no relevant deviation. This analysis will be conducted only if there are more than 5% subjects with relevant protocol deviations.
- ORR per BICR in treated subjects using treatment group “as treated” if more than 10% randomized subjects in any treatment group were never treated.
- ORR per BICR analysis for response evaluable subjects (randomized subjects with baseline and at least one on-study tumor assessment), if more than 10% randomized subjects in any treatment group were not response evaluable.
- ORR per BICR where all response designations contribute to the BOR determination, regardless of start of subsequent anti-cancer therapy.

To assess concordance between BICR and investigator assessments, BOR will be cross-tabulated by treatment group and assessment type (Investigator vs. BICR). Concordance Rate of Responders will be computed as the frequency with which Investigator and BICR agree on classification of a subject as responder/non responder as a proportion of the total number of subjects assessed within each treatment group.

### **7.5.1.3 Subset Analyses of ORR**

The influence of baseline and demographic characteristics on the treatment effect will be explored via exploratory subset analyses for the following factors using the primary definition of ORR per BICR.

- Age categorization (<65 vs. 65-<75 vs ≥75)
- Gender (Male vs. Female)
- Race(White, Black, Asian, Other)
- Region (North America vs. EU vs.ROW)
- ECOG performance status(0, 1)
- Disease stage at study entry (locally recurrent vs locally recurrent and metastatic vs metastatic)
- HPV p-16 status (oropharyngeal Cancer HPV Positive (including unknown primary with HPV Positive) vs oropharyngeal Cancer HPV Negative /non-oropharyngeal Cancer) (from IVRS)
- HPV p-16 status (oropharyngeal Cancer HPV Positive (including unknown primary with HPV Positive) vs oropharyngeal Cancer HPV Negative /non-oropharyngeal Cancer) (based on CRF data)
- Oropharyngeal Cancer HPV p-16 status (oropharyngeal Cancer HPV Positive vs oropharyngeal Cancer HPV Negative) (based on CRF data)
- PD-L1 status (expressing vs non-expressing/non-evaluable/indeterminate) (from IVRS)

- PD-L1 status (expressing, non-expressing, non-evaluable/indeterminate) (based on clinical database)
- Tumor associated immune cell PD-L1
- PD-L1 combined positive score (CPS)
- Tumor mutational burden
- Gene expression profile Platinum-refractory (yes/no) (from IVRS)
- Platinum-refractory (yes/no) (based on CRF data)
- Tobacco use (Former/Current, Never, Unknown)
- Alcohol use (Former, Current, Never, Unknown)
- Prior surgery (Yes, No)
- Prior radiotherapy (Yes, No)
- Site of primary tumor (Oral Cavity, Larynx, Oropharynx, Hypopharynx, Unknown P16 primary location, Other)
- Best response to the most recent regimen (CR/PR, SD, PD, Unknown or Not reported)
- Disease stage at initial diagnosis (stage I, II, III, IVA, IVB, IVC)
- Time from initial disease diagnosis to randomization (< 1 year, 1 - < 2 year, 2 - < 3 year, 3 - < 4 year, 4 - < 5 year, ≥ 5 year)

BICR-determined ORR along with the exact 95% CI using Clopper-Pearson method will be displayed for each treatment group. If a subset category has less than 10 subjects per treatment group, ORR will not be computed/displayed.

A forest plot of the unweighted ORR response rate differences (nivolumab/ipilimumab vs. nivolumab/ipilimumab placebo) and corresponding 95% CIs using the method of Newcombe will be produced for each level of the subgroups listed above.

#### **7.5.1.4 Duration of Objective Response**

Duration of response (DOR) curves in each treatment group will be estimated using KM product-limit method for subjects with a BOR of PR or CR per BICR assessment. Median DOR, corresponding two-sided 95% CI, and range will be calculated. Proportion of subjects with duration of response at least 6 months will be estimated with corresponding two-sided 95% CI. Summary statistics will be computed based on a log-log transformed CI for the survivor function.

#### **7.5.1.5 Time to Objective Response**

Summary statistics of time to objective response (TTR) will be provided for each treatment group for subjects who achieve PR or CR.

A by-subject listing will be presented including treatment arm, time to response, duration of response, whether the subject was censored for duration of response, and, if so, the reason.

[REDACTED]

### **7.5.2 Secondary Endpoint ORR in Platinum Eligible Subgroup**

The secondary endpoint of ORR in platinum eligible subgroup will be summarized by a binomial response rate and its corresponding two-sided 95% exact CI using Clopper-Pearson method for each treatment group. ORR will also be estimated in baseline subgroups as specified in [Section 7.5.1.3](#). DOR and TTR will be analyzed similarly as described in [Sections 7.5.1.4](#) and [7.5.1.5](#). Analyses described in [Sections 7.5.1.6](#) and [7.5.1.7](#) will also be performed similarly for platinum eligible subgroup.

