**8.4.2 Efficacy Analyses**

Efficacy analyses will be performed by treatment for each of platinum eligible and platinum refractory sub-group as randomized and for all randomized subjects.

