## 2.2 Treatment Assignment

After the subject's initial eligibility is established and informed consent has been obtained, the subject must be enrolled into the study by calling an interactive voice response system (IVRS) to obtain the subject number.

Once enrolled in the IVRS, subjects that have met all eligibility criteria will be ready to be randomized through the IVRS in a 2:1 ratio, with twice as many subjects receiving nivolumab and ipilimumab as nivolumab and ipilimumab-placebo:

- Arm A: Nivo 3 mg/kg Q2W + Ipi 1 mg/kg Q6W
- Arm B: Nivo 3 mg/kg Q2W + Ipi Placebo Q6W

The stratification factors are:

- Platinum refractory subgroup (yes vs no).
- PD-L1 status (expressing vs non-expressing or non-evaluable or indeterminate). PD-L1 status is set to expressing when tumor cell PD-L1 expression  $\geq 1\%$ . (up to 20% of randomized subjects can be included into the study as non-evaluable or indeterminate).
- HPV p-16 status (oropharyngeal Cancer HPV Positive (including unknow primary with HPV p16 positive) vs oropharyngeal Cancer HPV Negative /non-oropharyngeal Cancer).

The randomization procedures will be carried out via permuted blocks within each stratum. The exact procedures for using the IVRS will be detailed in the IVRS manual.

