### **3.2 Secondary**

- To estimate the ORR and assess DOR of the treatment of nivolumab in combination with ipilimumab vs nivolumab in combination with ipilimumab placebo, as determined by BICR using RECIST 1.1 criteria, for first line treatment of recurrent or metastatic SCCHN in the platinum eligible setting
- To assess progression-free survival (PFS), as determined by BICR, of nivolumab in combination with ipilimumab vs. nivolumab in combination with ipilimumab placebo for first line treatment of recurrent or metastatic SCCHN in the platinum eligible and platinum refractory settings, separately and overall
- To assess overall survival (OS), of nivolumab in combination with ipilimumab vs. nivolumab in combination with ipilimumab placebo for first line treatment of recurrent or metastatic SCCHN in the platinum eligible and platinum refractory settings, separately and overall
- To assess efficacy (ORR, DOR, PFS and OS) by PD-L1 expression of nivolumab in combination with ipilimumab compared to nivolumab in combination with ipilimumab placebo for first line treatment of recurrent or metastatic SCCHN in the platinum eligible and platinum refractory settings, separately and overall
- To assess efficacy (ORR, DOR, PFS and OS) by HPV p-16 status of nivolumab in combination with ipilimumab compared to nivolumab in combination with ipilimumab placebo for first line treatment of recurrent or metastatic SCCHN in the platinum eligible and platinum refractory settings, separately and overall

- To evaluate tumor mutation burden, as a potential predictive biomarker of efficacy (such as ORR, DOR, PFS and OS) of nivolumab in combination with ipilimumab or ipilimumab placebo for first-line treatment of recurrent or metastatic SCCHN in the platinum eligible and platinum refractory settings, separately and overall.

[REDACTED]

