#### 7.5.1.1 Primary Analysis of ORR

The comparison of ORR between nivolumab in combination with ipilimumab vs nivolumab in combination with ipilimumab placebo in platinum refractory randomized subjects will be carried out using a two-sided Cochran-Mantel-Haenszel (CMH) test stratified by the stratification factors PD-L1 status (expressing vs non-expressing/non-evaluable/indeterminate) and HPV p-16 status (oropharyngeal HPV p16 positive (including unknown primary with HPV p16 positive) vs oropharyngeal HPV p16 negative or nonoropharyngeal) as recorded in the IVRS. The significance level will be adjusted for an interim analysis which will be performed when around 70% of platinum-refractory subjects have been followed for at least 6 months after randomization. Using Lan-DeMets alpha spending function with O'Brien-Fleming boundaries, the significance level for this comparison will be determined by the fraction of subjects included in the interim analysis. If the analysis is performed when exactly 70% of platinum refractory subjects have reached 6 months follow up after randomization, the alpha level is 0.015 for the interim and 0.045 for the final. An associated odds ratio (nivolumab/ipilimumab vs. nivolumab/ipilimumab placebo) and corresponding CI will be calculated. ORR will be summarized by a binomial response rate and its corresponding two-sided exact CI using Clopper-Pearson method for each treatment group. An estimate of the difference in ORRs between arms (nivolumab/ipilimumab vs. nivolumab/ipilimumab placebo) and corresponding CI will be calculated using Cochran-Mantel-Haenszel (CMH) methodology and adjusted by the stratification factors as recorded in the IVRS.

The formula is

$$\hat{\theta} = \frac{\sum_i w_i \hat{\theta}_i}{\sum_i w_i} \sim N \left[ \theta, \frac{\sum_i w_i^2 \left[ \frac{p_{ix}(1-p_{ix})}{n_{ix}-1} + \frac{p_{iy}(1-p_{iy})}{n_{iy}-1} \right]}{\left( \sum_i w_i \right)^2} \right]$$

where  $\hat{\theta} = p_{ix} - p_{iy}$  is the difference in rates in the *i*th stratum,  $w_i = \frac{n_{ix}n_{iy}}{n_{ix} + n_{iy}}$ , and  $n_{ix}$  and  $n_{iy}$  are the number of subjects randomized to treatments x and y, respectively, in the *i*th stratum.

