### **7.5.3 Progression Free Survival**

#### **7.5.3.1 PFS primary analysis**

The PFS function based on BICR assessment for each treatment arm will be estimated using Kaplan Meier technique and will be displayed graphically in the platinum refractory and platinum eligible subgroups, separately. The primary definition of PFS will be used in this analysis ([Section 4.2.2](#)). Median Survival time along with 95% CI will be constructed based on a log-log transformed CI for the survivor function. The hazard ratio and the 95% confidence interval will be estimated in a stratified Cox proportional hazards model using the randomized arm as a single covariate, stratified by PD-L1 status and HPV p-16 status, in the platinum refractory and platinum eligible subgroups, separately. PFS rates at 3, 6, 12 and 24 months, with 95% CIs will be estimated using Kaplan-Meier methodology. Minimum follow-up must be greater than or equal to the time-point to generate the rate.

The source of PFS event as assessed by BICR (RECIST 1.1 progression or death) will be summarized by treatment group.

The status of subjects who are censored (as per primary definition of PFS) in the PFS KM analysis will be tabulated for each randomized treatment group using the following categories:

- On-study (on-treatment, follow-up)
- Off-study (lost to follow-up, withdrawn consent, never treated)
- Received subsequent anticancer therapy

- No baseline tumor assessment

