### **7.5.4 Overall Survival**

#### **7.5.4.1 Primary Analysis of Overall Survival**

OS distribution for each treatment arm will be estimated using Kaplan Meier technique and will be displayed graphically in the platinum refractory and platinum eligible subgroups, separately. Median Survival time in each arm along with 95% CI will be constructed based on a log-log transformed CI for the survivor function. The hazard ratio and the 95% confidence interval will be estimated in a stratified Cox proportional hazards model using the randomized arm as a single covariate, stratified by PD-L1 status and HPV p-16 status, in the platinum refractory and platinum eligible subgroups, separately. OS rates at 6, 9, 12, 18, 24, 36, 48 and 60 months with 95% CIs will be estimated using Kaplan-Meier methodology. These analyses will be performed only if the minimum follow-up for OS has been reached corresponding to that endpoint.

The status of subjects who are censored in the OS KM analysis will be tabulated for each randomized treatment group using the following categories:

- On-study (on-treatment, in follow-up)
- Off-study (lost to follow-up, withdrawn consent, never treated)

To examine the assumption of proportional hazards in the Cox regression model, in addition to treatment, a time-dependent variable, in the form of a treatment by time interaction, will be added into the model. A two-sided Wald Chi-square p-value of less than 0.1 may indicate a non-constant hazard ratio.

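### Does the SAP leave platinum-eligible ORR without a proper between-arm estimate?

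*SAP*

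**What the plan says.** The first secondary objective in SAP 3.2 is "To estimate the ORR and assess DOR of the treatment of nivolumab in combination with ipilimumab vs nivolumab in combination with ipilimumab placebo" in the platinum-eligible setting. SAP 7.5.2 implements it with an ORR "summarized by a binomial response rate and its corresponding two-sided 95% exact CI using Clopper-Pearson method for each treatment group". It then refers to 7.5.1.3 for baseline subgroups, to 7.5.1.4 and 7.5.1.5 for duration of and time to response, and to 7.5.1.6 and 7.5.1.7, whose text is redacted.

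For the platinum-refractory subgroup, SAP 7.5.1.1 goes further. It gives a CMH test, an odds ratio, and "An estimate of the difference in ORRs between arms" weighted over the PD-L1 and HPV p-16 strata. SAP 7.5.1.3 adds "A forest plot of the unweighted ORR response rate differences" with Newcombe 95% intervals for each level of a list of factors. Platinum-refractory status, yes or no, is one of them.

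For PFS, SAP 7.5.3.1 specifies a hazard ratio "stratified by PD-L1 status and HPV p-16 status, in the platinum refractory and platinum eligible subgroups, separately". SAP 7.5.4.1 has the OS hazard ratio "estimated in a stratified Cox proportional hazards model using the randomized arm as a single covariate", with the same stratification and the same split by subgroup. On randomisation, SAP 2.2 states: "The randomization procedures will be carried out via permuted blocks within each stratum".

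Two general defaults apply. Protocol 8.4.2 says: "Efficacy analyses will be performed by treatment for each of platinum eligible and platinum refractory sub-group as randomized and for all randomized subjects". SAP 7.5 has a similar sentence, subject to anything otherwise specified. SAP section 5 states that none of the secondary endpoints will be tested, and SAP 7.5 confines p-values to the refractory ORR comparison.

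**The concern.** The objective is worded as one regimen *versus* the other, yet the section that implements it names only two separate response rates. It cross-refers to almost every part of 7.5.1 except 7.5.1.1, the part that defines the stratified contrast. PFS and OS in the same patients do get a stratified contrast. On a quick reading, the only between-arm ORR figure left for the final platinum-eligible analysis is an unweighted difference in an exploratory forest plot.

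If that were a real gap, two things would be at stake. The report could lack one pre-designated treatment-effect estimate for the first-listed secondary objective, which leaves room to choose one afterwards. And because allocation is blocked within strata, an interval that ignores the strata could be wider than it needs to be when the strata predict response.

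**Working it through.** **1. What the design of this subgroup calls for**

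| | Platinum refractory | Platinum eligible |
|---|---|---|
| Objective (SAP 3.1, 3.2) | compare ORR | estimate ORR |
| Basis for size (SAP 5) | 84% power for an odds ratio, 144 and 72 subjects | width of the exact interval, 120 and 60 subjects |
| Test and p-value (SAP 5, 7.5) | yes | no |
| Stated ORR method | CMH test, odds ratio, stratified difference (7.5.1.1) | per-arm rate with exact interval (7.5.2) |

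The two columns differ consistently in every row. The method in 7.5.2 is the one on which the subgroup was sized.

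**2. The plan's own precision figure**

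Clopper-Pearson limits for x responders of n are Beta(0.025; x, n−x+1) and Beta(0.975; x+1, n−x).

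- 60/120: 40.7% to 59.3%. The rounded limits give 59.3 − 40.7 = 18.6 points, the stated maximum; the unrounded width is 18.53.
- 48/120: 31.2% to 49.3%. 12/60: 10.8% to 32.3%.
- All twelve rows of SAP Tables 5-1 and 5-2 reproduce to one decimal.

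**3. Is there a between-arm estimate?**

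Platinum status is constant within either subgroup, so as a forest-plot factor it only makes sense if the plot is run over all randomised subjects. The SAP 7.5 default allows that. The *no* level is then the whole platinum-eligible subgroup, with a named contrast and a named interval.

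Example with two rates taken from the SAP tables, 40% of 120 against 20% of 60:

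- Wilson limits: 31.7% to 48.9% and 11.8% to 31.8%.
- Newcombe lower limit: 20.0 − √[(40.0 − 31.7)² + (31.8 − 20.0)²] = 5.6 points.
- Newcombe upper limit: 20.0 + √[(48.9 − 40.0)² + (20.0 − 11.8)²] = 32.1 points.
- SAP 7.5.1.1 variance as a single stratum: SE = √(0.40·0.60/119 + 0.20·0.80/59) = 0.0688, so 20.0 ± 1.96·6.88 = 6.5 to 33.5 points.

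The widths are 26.5 and 27.0 points. Before stratification, the Newcombe interval is no worse.

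**4. What stratifying would change**

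Simulation of 180 subjects in four PD-L1 by HPV strata with shares 45/15/30/10%, 2:1 permuted blocks of 6, a within-stratum odds ratio of 2.0, and 20,000 trials per scenario. Shares, block size, odds ratio and stratum response rates are assumptions; the documents give none of them.

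| Control ORR by stratum (%) | Sampling SD, crude / stratified | Mean width, Newcombe / CMH (points) | Coverage, Newcombe / CMH (%) | 95th percentile of gap between estimates (points) |
|---|---|---|---|---|
| 20/20/20/20 | 0.0677 / 0.0677 | 26.0 / 26.3 | 95.0 / 94.4 | 0.4 |
| 25/30/12/15 | 0.0673 / 0.0673 | 26.2 / 26.2 | 95.1 / 94.5 | 0.6 |
| 30/45/8/20 | 0.0677 / 0.0676 | 27.3 / 26.4 | 96.1 / 94.8 | 0.9 |
| 35/60/5/20 | 0.0670 / 0.0669 | 28.1 / 25.9 | 96.7 / 94.3 | 1.2 |

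Two other sets of shares (50/8/36/6% and 40/25/22/13%) put the gap at 0.3 to 1.3 points. Over all sets, coverage is 95.0% to 96.8% for Newcombe and 94.3% to 95.0% for CMH. Blocking within strata already balances the arms, so the two estimators have practically the same sampling error. Only the reported interval moves: CMH is from 0.3 points wider to 2.2 points narrower, and it is clearly narrower only in the two scenarios where the assumed strata are strongly prognostic.

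**The case for a change.** The strongest case for a gap is that the authors wrote a stratified platinum-eligible contrast where they wanted one, for PFS and OS, and did not for ORR. The general default in SAP 7.5 yields to anything otherwise specified and names no method, and 7.5.2 does specify a method, so a programmer could reasonably leave out the stratified difference. The forest plot is labelled exploratory and takes platinum status from both IVRS and CRF, so it does not single out one estimate. The wording on similar descriptive analyses in platinum-eligible subjects covers the interim only. The PD-L1 interaction models give odds ratios by PD-L1 status, not for the whole subgroup.

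All of that describes the visible text correctly, and a cross-reference to 7.5.1.1 would make the ORR section read like the PFS and OS sections. It does not show an error. Nothing in either document requires a stratified ORR contrast in a subgroup that is estimated and not tested. Protocol 8.4.2.2, which the table of contents lists as the method for secondary and exploratory endpoints, and SAP 7.5.1.6 and 7.5.1.7, which 7.5.2 applies to this subgroup, are redacted, and text hidden by redaction cannot be counted as absent. The width argument also has limits. Newcombe coverage did not fall below 95.0% in these scenarios, so any excess width errs on the safe side. The stratified variance divides by n − 1 and would need a rule for a stratum with one subject in an arm, which occurs in 0% to 1.8% of simulated trials depending on the assumed shares.

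**Conclusion.** The concern does not hold. Per-arm rates with exact intervals match the objective, the sample-size basis and the decision not to test in this subgroup. A between-arm difference with a valid interval is available through SAP 7.5.1.3, and the general efficacy defaults can be read as extending 7.5.1.1 as well. No figure, test or decision rule is wrong. Choosing the stratified difference over the unweighted one would move the estimate by at most about 1.3 points in 95% of simulated trials, against an interval some 26 to 28 points wide, with no gain in precision. The size of these effects rests on assumed strata shares, block size, odds ratio and stratum response rates. The conclusion itself rests mainly on the text: the estimation objective, the per-arm sizing and the absence of a test. A matching sentence in 7.5.2 would be a matter of consistent presentation only.

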### **7.5.3 Progression Free Survival**

#### **7.5.3.1 PFS primary analysis**

The PFS function based on BICR assessment for each treatment arm will be estimated using Kaplan Meier technique and will be displayed graphically in the platinum refractory and platinum eligible subgroups, separately. The primary definition of PFS will be used in this analysis ([Section 4.2.2](#)). Median Survival time along with 95% CI will be constructed based on a log-log transformed CI for the survivor function. The hazard ratio and the 95% confidence interval will be estimated in a stratified Cox proportional hazards model using the randomized arm as a single covariate, stratified by PD-L1 status and HPV p-16 status, in the platinum refractory and platinum eligible subgroups, separately. PFS rates at 3, 6, 12 and 24 months, with 95% CIs will be estimated using Kaplan-Meier methodology. Minimum follow-up must be greater than or equal to the time-point to generate the rate.

The source of PFS event as assessed by BICR (RECIST 1.1 progression or death) will be summarized by treatment group.

The status of subjects who are censored (as per primary definition of PFS) in the PFS KM analysis will be tabulated for each randomized treatment group using the following categories:

- On-study (on-treatment, follow-up)
- Off-study (lost to follow-up, withdrawn consent, never treated)
- Received subsequent anticancer therapy

- No baseline tumor assessment

### **7.5.3.2 Sensitivity Analyses of Progression Free Survival**

The following sensitivity analyses will be conducted using the primary definition of PFS in the randomized subjects:

- PFS per BICR using stratification factors as obtained from the baseline CRF pages and clinical database (instead of IVRS). The hazard ratio associated with treatment will be presented along with the associated two-sided 95% CIs. This analysis will be performed only if the stratification variable/factor at randomization (as per IVRS) and baseline are not concordant for at least 10% of randomized subjects.
- PFS per BICR using an un-stratified Cox model. The hazard ratio associated with treatment will be presented along with the associated two-sided 95% CIs.
- The primary PFS per BICR analysis will be repeated using secondary PFS definition which accounts for the tumor scans post subsequent therapies. The hazard ratio associated with treatment and median PFS will be presented along with the associated two-sided 95% CIs.

A by-subject listing for all randomized subjects will be presented including treatment arm, IVRS stratification level, PFS under the primary definition with censoring status and reason, PFS under the secondary definition with censoring status and reason.

